### Secondary Endpoints

Secondary endpoints include:

- NPV and PPV overall
- Likelihood ratios overall
- Method concordance against Access BNP assay

There are no pass/fail criteria for secondary endpoints

### Additional Endpoints

Additional endpoints include but are not limited to:

- Assay performance in different subgroups (eg: age, sex, comorbidities)
- Descriptive statistics for subjects with comorbidities
- Descriptive statistics by NYHA classification

Acceptable assay performance data are defined in respective assay design input document(s) (DIDs) and external assay performance requirements.

 BECKMAN COULTER	Access BNP Clinical Performance Evaluation Statistical Analysis Plan	Document #: NA
------------------------------------------------------------------------------------------------------	---------------------------------------------------------------------------------	--------------------------

## Study Design and Sample Size

### Study Design

This is a prospective-multicenter controlled clinical study to evaluate diagnostic accuracy and ability to assess heart failure severity of the Access BNP assay. A one-time blood sample is collected from consented and enrolled subjects, within 4 hours of presentation, representing the intended use population (adult subjects presenting with clinical suspicion of new onset heart failure or worsening symptoms suggestive of decompensated or exacerbated heart failure).

Clinical performance of the Access BNP Assay will be evaluated as an aid in the diagnosis and assessment of severity in adults suspected of having new onset heart failure or decompensated or exacerbated heart failure. Diagnostic parameters (i.e., sensitivity and specificity) will be defined by subjects' HF status as indicated by the IUO assay relative to the subjects' final clinical HF status.

### Patient Enrollment

Individuals presenting with clinical suspicion of heart failure will be enrolled in the study. Subjects will be considered enrolled when informed consent is obtained via a signed and dated Institutional Review Board (IRB) approved Informed Consent Form (ICF).

### Participating Centers

Study enrollment and blood sample collection are conducted at a minimum of 5 and a target of approximately sixteen (16) to eighteen (18) geographically diverse U.S. clinical research sites with Emergency Departments and/or Outpatient Clinics. All clinical sites follow the same enrollment protocol Access BNP Clinical Subject Sample Collection Enrollment Study Protocol (BNP-05-24) (EDMS title "Access BNP Clinical Enrollment Study").

### Sample Testing

Specimens are to be collected in K2 EDTA plasma tubes. Collected samples will be tested, within 60 days of blood collection, at external clinical sites under the testing protocol Access BNP on Dxi 9000 Clinical Performance Evaluation: Specimen Testing and Clinical Concordance Study (BNP-02-23) (EDMS title "Access BNP Clinical Performance Evaluation: Testing and Clinical Concordance Study").

### Sample Size

Assuming an expected performance of IUO Access BNP assay of 82% sensitivity, 400 HF positive subjects can provide > 92% power to claim sensitivity of 82% with a lower bound

 BECKMAN COULTER	Access BNP Clinical Performance Evaluation Statistical Analysis Plan	Document #: NA
------------------------------------------------------------------------------------------------------	---------------------------------------------------------------------------------	-------------------

confidence interval of 75%. Additionally, 600 HF negative subjects can provide > 98% power to claim specificity > 98% with a lower bound confidence interval of 95%. Thus, with an assumed 40% prevalence and 10% attrition rate the total sample size is expected to be 1,100 subjects.

The following table depicts the sample size by potential rates of prevalence:

HF Prevalence	# of Subjects HF +	# of Subjects Total
30%	400	1333
40%	400	1000
50%	400	800

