15.6. Reconciliation of Study Material, Supplies and Samples

Sponsor is to supply enough quantities of study materials, supplies, and samples to enable the site to complete the study. The site is required to maintain the inventory of these materials provided and document the reconciliation of these materials.

At the completion of this clinical study, all unused materials, supplies, and samples must be returned to the sponsor or disposed of according to instructions from the sponsor. If materials are disposed at the study site, the Investigator must provide the sponsor with a signed record of disposition.

16. Statistical Considerations

The number of K2 EDTA individual subject samples used in this testing study will be approximately 1100.

All valid testing results of samples collected under protocol BNP-05-24 Access BNP Clinical Subject Sample Collection Enrollment Study Protocol from subjects presenting with a clinical suspicion of new onset heart failure or worsening symptoms suggestive of decompensated or exacerbated heart failure will be included in analysis.

Primary endpoints of the study will be diagnostic accuracy between final clinical site diagnosis (HF and Non-HF), IUO BNP assay testing results and severity assessment utilizing the NYHA class.

Method concordance will be established using the valid testing data from the investigational device Access BNP Assay (**item number D06227**) for Dxl 9000 Access Immunoassay Analyzer (P/N C11137) against the currently marketed Access BNP Assay (**item number 98200, original formulation**) for Access 2 Immunoassay System (P/N 81600N). Positive percent agreement (PPA) and Negative percent agreement (NPA) will be calculated using the data.

The objective is to validate established diagnostic cutoff (rule-out) and assess HF severity on the IUO Access BNP Assay (**item number D06227**) using the Dxl 9000 Access Immunoassay Analyzer (P/N C11137). Corresponding sensitivity and specificity at this cutoff will be established for the intended use population. Diagnostic parameters (i.e., sensitivity, specificity, NPV, and PPV) will be

 BECKMAN COULTER	Access BNP Clinical Performance Evaluation: Testing and Clinical Concordance Study	Document BNP-02-23 Protocol Version: 2.7
---	---	---

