### Primary Endpoints

Primary endpoints of the study will be diagnostic accuracy measured in proportions of sensitivity and specificity between Access BNP assay and final clinical HF status (determined by site diagnosis) and severity assessment measured by correlation between assay results and the New York Heart Association (NYHA) classification.

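### The SAP's table of sample size by prevalence is 400/prevalence only, so its 50% row (800) leaves 400 of the 600 HF-negative subjects and specificity power of about 89%, not above 98%

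*SAP*

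**What the plan says.** The SAP's Primary Endpoints section makes both accuracy measures primary: "Primary endpoints of the study will be diagnostic accuracy measured in proportions of sensitivity and specificity".

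The Sample Size section treats each in turn. For sensitivity, with 82% expected, "400 HF positive subjects can provide > 92% power to claim sensitivity of 82% with a lower bound" of 75%. For specificity, "600 HF negative subjects can provide > 98% power to claim specificity > 98"%, with a lower limit of 95%. The total follows from these two counts: "with an assumed 40% prevalence and 10% attrition rate the total sample size is expected to be 1,100 subjects".

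The section closes with a table introduced by "The following table depicts the sample size by potential rates of prevalence". Its columns are prevalence, HF-positive subjects and total subjects. HF-positive is 400 in every row, and the totals are 1333, 1000 and 800 at 30%, 40% and 50%. There is no HF-negative column and no note that the totals serve sensitivity alone.

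The protocol carries the same overall size in section 16 (Statistical Considerations): "The number of K2 EDTA individual subject samples used in this testing study will be approximately 1100".

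**The concern.** Two counts are set above the table, but only one of them is used in it. As prevalence rises, HF-positive subjects become easier to find and HF-negative subjects harder. A table driven by the HF-positive count alone therefore shows the required total falling steadily. A reader would conclude that at 50% prevalence 800 subjects are enough. In fact the HF-negative count becomes the binding one above 40%, and the total needed goes up.

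At stake is the power for specificity, a primary endpoint, in one of the three scenarios that the SAP itself chose to show. The SAP is meant to support regulatory submissions, so its sample-size justification should not contradict itself.

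**Working it through.** **Inputs.** From the SAP, Sample Size: sensitivity 82% against a lower limit of 75%, n = 400, power above 92%; specificity 98% against a lower limit of 95%, n = 600, power above 98%; prevalence 40%, attrition 10%, total 1,100; table totals 1333, 1000, 800. From the SAP, Statistical Methods (Primary and Secondary Endpoints): a two-sided 95% score interval. The Sample Size section names no alpha or interval of its own, so using the score interval here is an assumption. It puts the lower limit at one-sided 0.025.

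**Step 1: reproduce the stated powers.** Normal formula with null variance at the critical value:

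power = Φ( [ (p1 − p0)·√n − 1.96·√(p0(1 − p0)) ] / √(p1(1 − p1)) )

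- Sensitivity, n = 400: (0.07 × 20 − 1.96 × √0.1875) / √0.1476 = 1.435, power 92.4%. Exact binomial with the score limit: 93.1%.
- Specificity, n = 600: (0.03 × 24.495 − 1.96 × √0.0475) / 0.14 = 2.198, power 98.6%. Exact: 97.98%.

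Both stated figures reproduce to within rounding.

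**Step 2: reproduce the table.** 400/0.30 = 1,333.3; 400/0.40 = 1,000; 400/0.50 = 800. All three totals match 400/prevalence.

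**Step 3: HF-negative subjects implied by each row** (total minus 400).

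| Prevalence | Table total | HF-negative | Against 600 |
|---|---|---|---|
| 30% | 1,333 | 933 | met |
| 40% | 1,000 | 600 | met exactly |
| 50% | 800 | 400 | 200 short |

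In general the implied count is 400(1 − p)/p, which is below 600 for every p above 0.40.

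**Step 4: specificity power in the 50% row.** n = 400: (0.03 × 20 − 1.96 × √0.0475) / 0.14 = (0.600 − 0.427) / 0.14 = 1.234, power 89.1%. Exact: at least 389 of 400 must be correctly negative for the score lower limit to exceed 95%, and the chance of that at a true 98% is 89.0%.

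**Step 5: totals that meet both counts.** Evaluable total = max(400/p, 600/(1 − p)).

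- 30%: max(1,333.3; 857.1), rounded up to 1,334
- 40%: max(1,000; 1,000) = 1,000
- 50%: max(800; 1,200) = 1,200

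**Step 6: the planned 1,100.** 1,100 × 0.90 = 990 evaluable. Exact power, normal formula in brackets:

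| Prevalence | HF-positive | Sensitivity power | HF-negative | Specificity power |
|---|---|---|---|---|
| 30% | 297 | 82.0% (82.4%) | 693 | 99.2% (99.5%) |
| 40% | 396 | 92.7% (92.2%) | 594 | 98.2% (98.5%) |
| 50% | 495 | 96.2% (96.7%) | 495 | 95.6% (95.7%) |

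Exact power moves in small steps with n, so these are best quoted to the nearest point.

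**The case against.** The best defence is that the table does just what its columns show: the total needed to reach 400 HF-positive subjects at each prevalence. No row carries a power claim, and the SAP says that 600 HF-negative subjects can give the stated power, not that 600 is a minimum. The total is tied expressly to 40% prevalence, and nothing provides for stopping at 800 or re-sizing on observed prevalence.

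Much of this stands. The division is correct, the planned size is unaffected, and the 89% describes an 800-subject study that nobody intends to run. What does not stand is the reading of the table as HF-positive only. Its lead-in presents it as the sample size by prevalence, its last column is the total, and it follows directly on a paragraph that uses both counts to arrive at a total.

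The 89% also depends on the interval. With a one-sided 0.05 limit, exact score power at n = 400 is 93.8%, still below 98%. An alternative-variance Wald formula gives 99.0%. That formula, however, gives 95.4% and 99.95% for the two stated powers, well above the SAP's figures, and it is not the SAP's interval.

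**Conclusion.** The point holds and is minor. The table leaves out the HF-negative count, and its 50% row falls 200 subjects short of it, with specificity power of about 89% where the text above quotes more than 98%. The shortfall in subjects is plain arithmetic; the power figure assumes a true specificity of 98%, a limit of 95% and the SAP's two-sided 95% score interval.

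A reader might infer three stronger things that the documents do not support:

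- **That the table also forgets attrition**, so that 800 enrolled would leave fewer still. The 40% row shows 1,000 beside a sentence that reaches 1,100 with attrition, so the rows are evidently before attrition. They only lack a label.
- **That the planned 1,100 is wrong.** At the assumed 40% it gives about 93% and 98% power, in line with the text. At 50%, specificity power is about 96%, a small drop.
- **That the plan hides a shortfall at 30%.** The 1,333 row already shows that 1,100 is too few for 400 HF-positive subjects there. Only the resulting sensitivity power, about 82%, is not stated.

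**What to change.** In the SAP's Sample Size section:

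1. Replace the totals with max(400/prevalence, 600/(1 − prevalence)) evaluable subjects: 1,334 / 1,000 / 1,200 at 30/40/50%.
2. Add an HF-negative column (934 / 600 / 600) and show the HF-positive count that goes with each total (400 / 400 / 600).
3. Label the totals as evaluable subjects, before attrition.
4. Add a sentence saying that the quoted powers apply at about 40% prevalence, and that with the planned 1,100 (990 evaluable) approximate power at 30/40/50% is 82/93/96% for sensitivity and 99/98/96% for specificity, naming the score interval as the basis.

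The cost is one table and one sentence. Planned enrolment stays at about 1,100, no subjects are added and no analysis changes. The price is that the SAP then shows openly that power is lower for sensitivity at 30% and for specificity at 50%.

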### Potential Bias and Measures Used to Prevent Bias

This is a typical diagnostic device evaluation study with a single arm and no active intervention. The test assay determines and reports numerical BNP measurements on fully automated instruments. HF status determined based on the IUO test result are compared to the true HF clinical status.

In addition, the following requirements are strictly followed to prevent and minimize potential biases:

- Any results deemed valid per the instruments' instruction for use cannot be excluded for any reasons other than documented human errors
- Retest only allowed on samples without valid results
- Discrepancy resolution information may be obtained on individual cases for learning purpose only. Such information is not to be used in any forms of statistical calculation.

### Internal/External Validity Verification

1. For sample representativeness, demographic information on all prospectively enrolled subjects in the Diagnostic Accuracy Study will be reported.
2. The Diagnostic Accuracy Study is a prospective controlled study with detailed inclusion/exclusion criteria, major subpopulations are the prespecified age groups. Samples will be tested randomly in experienced clinical laboratories with identical reagents and automated instruments provided by the sponsor. Data poolability is assumed and poolability analysis among 3 external testing sites, will not be performed in this study
3. Sample accountability will be examined and reported. All efforts will be made to prevent missing data. Missing data is expected to be rare. Missing data analysis

 BECKMAN COULTER	Access BNP Clinical Performance Evaluation Statistical Analysis Plan	Document #: NA
------------------------------------------------------------------------------------------------------	---------------------------------------------------------------------------------	--------------------------

will only be performed if missing data appears to be an issue affecting the study conclusion.

4. Missing data imputation will not be attempted.

## Statistical Methods

### Primary and Secondary Endpoints

Sensitivity, specificity, NPV, PPV, and likelihood ratios (positive and negative) of the Access BNP assay will be evaluated by comparing the Access BNP assay results to the final clinical site diagnosis.

The following are definitions of diagnostic accuracy for the IUO Access BNP assay.

IUO Access BNP assay result		Final clinical site diagnosis (HF Status)	
		HF Positive	HF Negative
≥ Respective Cutoff	TP (a)	FP (c)	
< Respective Cutoff	FN (b)	TN (d)	

TP: true positive; FP: false positive; TN: true negative; FN: false negative.

Estimates of sensitivity and specificity are calculated as:

$$Sensitivity = 100 \times \frac{a}{a + b}$$

$$Specificity = 100 \times \frac{d}{c + d}$$

$$PPV = 100 \times \frac{a}{a + c}; \quad NPV = 100 \times \frac{d}{b + d}$$

$$LR^+ = \frac{sen}{1 - spc} = \frac{a/(a + b)}{c/(c + d)}$$

 BECKMAN COULTER	Access BNP Clinical Performance Evaluation Statistical Analysis Plan	Document #: NA
------------------------------------------------------------------------------------------------------	---------------------------------------------------------------------------------	--------------------------

$$LR^- = \frac{1 - sen}{spc} = \frac{b/(a + b)}{d/(c + d)}$$

All enrolled subjects with valid Access BNP (P/N D06227) assay test result and final clinical site diagnosis will be included in the diagnostic accuracy endpoint analysis, *i.e.*, per protocol analysis. Point estimate, event counts, and a 2-sided 95% Score confidence interval will be reported.

### **Severity Assessment Study**

Statistical significance of positive correlation between medians of the Access BNP assay results and NYHA class will be tested using the Jonckheere-Terpstra test. Medians of BNP values, measured by Access BNP assay, of subjects in NYHA HF class I, II, III, and IV will be reported.

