defined by subjects' HF status as indicated by the IUO assay(s) relative to subjects' clinical HF diagnosis. Additionally, correlation between Access BNP assay results and severity (NYHA class) will be evaluated using the Jonckheere-Terpstra test. Point estimates, event counts, and a 2-sided 95% score confidence interval will be reported for all relevant endpoints.

In addition to the endpoint results, descriptive statistics such as mean median, standard deviations are to be reported. The results are used to support regulatory submissions for the Access BNP assay in all geographic regions, including but not limited to the European Union and United States (US).

The following requirements are strictly followed to prevent and minimize potential biases:

- Any Dxl 9000 results deemed valid per the instruments' instruction for use cannot be excluded for any reasons other than documented human errors.
- Access 2 valid result can only be excluded from analysis in the case a retest is needed on Dxl 9000 and outside of the 2-hour window of sample removal from the -70C (or colder) freezer. In this case a new sample is thawed and tested on both Dxl 9000 and Access 2. The first Access 2 valid result would be excluded from analysis.
- Discrepancy resolution information may be obtained on individual cases for learning purpose only. Such information is not to be reported in any forms of estimation or statistics.

17. Study Materials

The study materials and supplies that will be provided by Beckman Coulter are:

- Testing Specimen/Samples
- IUO Reagent kits for Beckman Coulter Dxl 9000 Access Immunoassay Analyzer*
- IVD Reagent kits for Beckman Coulter Access 2 Immunoassay System
- IVD Calibrators
- IVD Quality Controls
- Clinical Study Binder – eTMF Florence
- USB Flash Drives (if applicable)
- Dxl 9000 consumables (as needed)

* Inventory of Investigational Use Only (IUO) material must be maintained, and reconciliation procedures provided by Sponsor after study completion must be followed.

Basic lab equipment and supplies are not provided by sponsor such as centrifuges, pipettors, lab coats and gloves. Such supplies are part of site lab operation at the oversight of the Primary Investigator.

 BECKMAN COULTER	Access BNP Clinical Performance Evaluation: Testing and Clinical Concordance Study	Document BNP-02-23 Protocol Version: 2.7
---	---	---

18. Supplemental Materials Provided

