## Endpoints

The following measurements will be reported and evaluated for acceptable performance.

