### **Method Concordance Study**

Method concordance between Access BNP on the Dxl 9000 Immunoassay Analyzer (P/N D06227) and Access BNP on Access 2 (P/N 98200) (predicate) will be calculated based on the 100 pg/mL cutpoint. Positive Percent Agreement (PPA) and Negative Percent Agreement (NPA) will be evaluated independently. Point estimates and confidence intervals will be reported for all estimates.

$$PPA = 100 \times \frac{\# \text{ of samples above cutpoint for both test and comparator assays} *}{\# \text{ of samples above cutpoint by comparator assay} *}$$

$$NPA = 100 \times \frac{\# \text{ of samples below cutpoint for both test and comparator assays} *}{\# \text{ of samples below cutpoint by comparator assay} *}$$

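### Does the primary severity endpoint need an association estimate with an interval, and a stated population, beyond the planned Jonckheere-Terpstra test?

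*SAP*

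**What the plan says.** The SAP, under Primary Endpoints, includes "severity assessment measured by correlation between assay results and the New York Heart Association (NYHA) classification". Its Endpoints section opens with "The following measurements will be reported and evaluated for acceptable performance".

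The method is in the SAP, Severity Assessment Study. The first sentence is "Statistical significance of positive correlation between medians of the Access BNP assay results and NYHA class will be tested using the Jonckheere-Terpstra test". The second is "Medians of BNP values, measured by Access BNP assay, of subjects in NYHA HF class I, II, III, and IV will be reported". Additional Analyses adds descriptive statistics by NYHA class and, where appropriate, SD, IQR and the 5th and 95th percentiles.

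Protocol section 16 agrees on the test: "correlation between Access BNP assay results and severity (NYHA class) will be evaluated using the Jonckheere-Terpstra test". The next sentence there reads "Point estimates, event counts, and a 2-sided 95% score confidence interval will be reported for all relevant endpoints".

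On who is analysed, the SAP's inclusion sentence applies to subjects whose valid result and "final clinical site diagnosis will be included in the diagnostic accuracy endpoint analysis". Protocol section 16 includes all valid results from subjects with suspected heart failure. The SAP rules out imputation. Neither document states separately which subjects enter the severity test.

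**The concern.** The endpoint is defined as a correlation, yet no correlation coefficient or other trend estimate is named. A p-value mixes the strength of the gradient with the number of subjects, so by itself it cannot tell a weak gradient from a strong one. The intended use in Protocol section 3.6 includes aid in assessing severity, so strength matters.

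The contrast with method concordance sharpens the impression. That is a secondary endpoint without pass/fail criteria, and for it "Point estimates and confidence intervals will be reported for all estimates". The interval promised in Protocol section 16 is a score interval, which is a method for proportions and does not attach to a trend statistic or a median.

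The population is also loose. Using the counts in the SAP, Sample Size, the test could rest on about 400 heart-failure-positive subjects or on up to 1,000 evaluable subjects. A choice made after seeing data would weaken a primary analysis.

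**Working it through.** **The plan's own figures.** None is given for severity. The SAP's power figures concern sensitivity and specificity, and they reproduce by the normal approximation at two-sided 0.05:

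- Sensitivity, n = 400: (0.07 − 1.96 × √(0.75 × 0.25/400)) / √(0.82 × 0.18/400) = 0.02757/0.01921 = 1.435, power 92.4% (stated: above 92%).
- Specificity, n = 600: (0.03 − 1.96 × √(0.95 × 0.05/600)) / √(0.98 × 0.02/600) = 0.01256/0.00572 = 2.198, power 98.6% (stated: above 98%).
- Total before attrition: 400/0.40 = 1,000.

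So 400 and 1,000 are used below as the two candidate sizes.

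**Assumptions not in the documents.** One-sided 0.025 (the upper half of a two-sided 0.05 test), no ties in BNP, and NYHA mix I to IV of 5/25/45/25% unless stated.

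**How small a trend reaches significance.** Let P = (N² − Σn²)/2 be the number of between-class pairs and Var(J) = [N²(2N+3) − Σn²(2n+3)]/72.

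- N = 400 (20, 100, 180, 100): P = 53,600; SD(J) = √(112,641,600/72) = 1,250.8. Required share of correctly ordered pairs: 0.5 + 1.96 × 1,250.8/53,600 = 0.546. With 400 × 399/2 = 79,800 pairs in all, tau-b = 2 × 1.96 × 1,250.8 / √(53,600 × 79,800) = 0.075.
- N = 1,000 (50, 250, 450, 250): P = 335,000; SD(J) = 4,939.9. Required share 0.529; tau-b = 0.047.

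Over four assumed class mixes the ranges are 0.073–0.076 and 0.046–0.048. One value of z, 4.71, corresponds to tau-b 0.075 × 4.71/1.96 = 0.180 at 400 and 0.047 × 4.71/1.96 = 0.114 at 1,000. The premise that a p-value alone does not show strength is correct.

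**Whether the test is sound.** Simulated with no trend (2,000 runs each, two-sided 0.05), it rejected in 4.3% and 5.1% of runs at 400 and 1,000. With an equal class mix the figures were 5.2% and 4.9%.

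**What an added tau-b would give.** At 400 subjects, steps of 0.2, 0.3 and 0.5 SD of log BNP per class give:

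| Step | Power | Mean tau-b (95% interval) |
|---|---|---|
| 0.2 SD | 90% | 0.12 (0.05–0.20) |
| 0.3 SD | over 99% | 0.18 (0.11–0.25) |
| 0.5 SD | 100% | 0.29 (0.22–0.36) |

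- *It is recoverable from planned output.* Tau-b = 2 × z × SD(J) / √(P × N(N−1)/2) needs only the test statistic and the class counts. The null standard error gives a half-width of 0.075 at 400, so 0.18 ± 0.075 is 0.105 to 0.255, close to the 0.11–0.25 above.
- *It depends on class mix.* A 0.5 SD step gives 0.27 to 0.37 over the four mixes, and a 0.3 SD step 0.165 to 0.237. The top of one range is near the bottom of the other.

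**What the planned medians give.** With an assumed SD of log BNP of 1.2, the class IV to class II median ratio (two steps) is exp(2 × 0.2 × 1.2) = 1.6 for the weak gradient and exp(2 × 0.5 × 1.2) = 3.3 for the strong one. Each of these medians, at 100 subjects, has a half-width of about 0.27 SD, so their difference has about √2 × 0.27 = 0.38 SD. The two gradients differ by 1.0 − 0.4 = 0.6 SD on that contrast. The medians also show shape: with assumed medians of 100, 250, 500 and 400 pg/mL, the test is significant in 99% of runs although class IV lies below class III. Tau-b would not reveal that; the medians would.

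**Population.** At an assumed median ratio of 1.2 per class, power (two-sided 0.05) is 68% with 400 subjects and 97% with 1,000. At a ratio of 1.3 it is 93% and over 99%.

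**The case for a change.** The strongest case is this. A primary endpoint defined as a correlation should be estimated with its precision, at the cost of one paragraph and a few validated lines of SAS. At a fixed class mix, a tau-b interval separates a 0.2 SD from a 0.5 SD gradient, while the p-value is significant in 90% or more of trials for both. Reporting rules for proportions do not fill the gap. Admitting subjects without heart failure could also let diagnosis, rather than severity, drive part of the trend.

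What stands: no summary estimate or interval is named, and the heart failure status of the analysed subjects is open.

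What does not stand is that the reader is left with a p-value alone. Medians by class are a firm commitment, with further descriptive statistics by class. Method concordance gets intervals because it consists of proportions with no planned test, so the contrast says little. The interval sentence in Protocol section 16 follows directly on the Jonckheere-Terpstra sentence. It is imprecise drafting, but it points towards reporting precision.

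The population gap is narrower than it looks. The SAP refers to subjects in an NYHA heart failure class, its objective is heart failure severity, and imputation is excluded, so a subject without a class cannot enter. If class is recorded only in subjects with heart failure, the two readings coincide. The enrolment protocol, BNP-05-24, may settle this; it is not among the documents reviewed.

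**Conclusion.** No change to the plan follows. This is missing reporting detail that analysts can fill sensibly. Followed as written, the SAP gives a valid trend test and class medians that show how large the gradient is and whether it is monotone. An added tau-b with an interval would be a convenience: it restates the test statistic on another scale, and its value moves with class mix. Naming the severity population is a one-sentence clarification worth recording before the data are analysed. On either reading the test keeps its size; power in the illustration moves from 68% to 97% at a ratio of 1.2 per class.

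The wording about correlation between medians is loose, since the test compares ordered distributions, but it misleads no one about what will be run.

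These sizes rest on assumed class mixes, gradients, SD and significance level, none of which the documents give. Acceptance criteria sit in design input documents that were not available, so nothing is concluded about what would count as success for this endpoint.
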